6.12.7. Immunogenicity

Blood samples for immunogenicity testing will be collected to determine antibody production against insulin lispro for all enrolled patients since Visit 2 prior to the first dose of study-provided prandial insulin treatment. Therefore, the blood sample result at Visit 2 will be considered as the anti-insulin lispro level at baseline for this study.

Patients who complete the 4-week safety follow-up visit (Visit 801) and have treatment-emergent anti-insulin lispro antibodies that have not returned to prespecified baseline range (Visit 2) will be asked to participate in follow-up to monitor antibody levels. The assessment of immunogenicity will include analyses of treatment-emergent anti-insulin lispro antibody up to Visit 801 and analyses of anti-insulin lispro antibody return to baseline during the insulin lispro antibody safety follow-up period.

6.12.7.1. Treatment Emergent Anti-Insulin Lispro Antibody

The treatment-emergent anti-insulin lispro antibody (denoted as treatment-emergent antidrug antibody [TEADA] throughout this SAP) is based on the change from baseline (Visit 2) to post-baseline (post-Visit 2) in the anti-insulin lispro antibody level (percent binding). Treatment-emergent antidrug antibody can be sub-classified as either treatment-induced (not detected anti-

insulin lispro antibody at baseline) or treatment-boosted (detected anti-insulin antibody at baseline):

- CCI [REDACTED]

- CCI [REDACTED]

The TEADA status during the analysis period will be determined using all data in the corresponding analysis period regardless of IP use. The summary for TEADA status and the anti-insulin lispro antibody level will use the same analysis data.

The number and percentage of patients with positive TEADA response during the analysis period of Visit 2 to Visit 801 will be summarized by treatment group. For patients with positive TEADA response any time during the analysis period, the number and percentage of patients with positive insulin cross-reactivity anytime during the analysis period, and the number and percentage of patients not meeting the TEADA criteria at Visit 801 will also be summarized by treatment group. Treatment groups will be compared by Fisher's exact test.

Both actual and change from baseline (Visit 2) for the anti-insulin lispro antibody level in percent binding will be summarized by scheduled visit prespecified in the protocol for patients with positive TEADA response from Visit 2 to Visit 801. The repeated measurement from Visit 2 to Visit 801 will be analyzed by an MMRM model with treatment, baseline value of the response variable, visit, and visit by treatment interaction as fixed factors and patient as the random factor. The ANCOVA model using treatment and baseline value as covariates will be used for the analysis of last non-missing observation prior to or at Visit 801 and the analysis of maximum percent binding during the analysis period of Visit 2 to Visit 801.

A listing of anti-insulin lispro antibody at each visit will be provided. The listing will include anti-insulin lispro antibody status (detected/not detected), anti-insulin lispro antibody percent binding, TEADA status (positive/negative), insulin cross-reactivity status, and insulin cross-reactivity percent binding for the safety population.

Subgroup analysis for the following selected efficacy and safety variables will be performed by the TEADA status during the analysis period of Visit 2 to Visit 801:

- HbA1c and change from baseline in HbA1c
- 1-hour and 2-hour PPG excursions
- basal, prandial, and total insulin dose
- treatment-emergent injection site reaction and hypersensitivity reaction
- event rate of overall hypoglycemic events

The analyses for HbA1c and change from baseline in HbA1c will be performed using an MMRM model for the primary analysis and the HbA1c data prior to permanent discontinuation

of IP. The model will include additional fixed terms of subgroup, subgroup by treatment interaction, subgroup by visit interaction, and 3-way interaction of treatment, subgroup and visit.

The PPG excursions will be analyzed by the ANCOVA model same as the model specified in Section 6.11.2 using the efficacy estimand. The model will include additional terms of subgroup, subgroup by treatment interaction, subgroup by visit interaction, and 3-way interaction of treatment, subgroup and visit.

The subgroup analysis for insulin dose will use the MMRM model specified in Section 6.11.5 using the efficacy estimand. The model will include additional fixed terms of subgroup, subgroup by treatment interaction, subgroup by visit interaction, and 3-way interaction of treatment, subgroup and visit.

The treatment-emergent injection site reaction and hypersensitivity reaction will be analyzed by a logistic regression model including terms of treatment, subgroup, treatment by subgroup interaction. All data regardless of IP use will be used for this analysis.

The negative binomial regression model specified in Table 6.6 with additional terms of subgroup, treatment by subgroup interaction will be used for the subgroup analysis of overall hypoglycemia event rate while on IP.

The interaction effects (3-way for MMRM and 2-way for ANCOVA/logistic regression model/negative binomial regression model) will be evaluated using a significance level of 0.10, unadjusted. If the interaction effect is significant ($p < 0.10$), separate analysis without the terms related with the subgroup will be performed for each subpopulation.

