Patients treated with insulin aspart, insulin glulisine, regular insulin, or premixed insulin will be transferred to insulin lispro at Visit 2 so that all patients will be treated with insulin lispro throughout the lead-in period. Patients treated with 1 to 2 prandial injections a day or premixed insulin prior to study entry will transition to 3 injections a day of prandial insulin lispro at the beginning of the lead-in period. At Visit 8, patients will be randomized to either LY900014 or insulin lispro at each meal. During the initial 12 weeks after randomization (intensive titration period), prandial insulin doses should be titrated as necessary in order to meet the target self-monitored blood glucose (SMBG) levels. Basal insulin may be titrated as needed to facilitate optimal prandial dosing or for safety reasons such as hypoglycemia or unacceptable hyperglycemia. Thereafter, during the maintenance period (Weeks 12-26 of treatment), it is

expected that adjustments to prandial and basal insulin doses would be to maintain glycemic control or for safety reasons such as hypoglycemia or unacceptable hyperglycemia.

Figure ITRN.1 illustrates the study design.

Abbreviations: T = telephone visit; wk = week.

- At Visit 2, patients treated with insulin aspart, insulin glulisine, regular insulin, or premixed insulin will be transferred to insulin lispro. At Visit 2, patients treated with a basal insulin regimen other than insulin glargine U-100 or insulin degludec will be transferred to an allowed study basal regimen of insulin glargine U-100 once or twice daily or insulin degludec U-100 or U-200 once daily. At Visit 8, patients will be randomized to either insulin lispro or LY900014 and continue their basal insulin regimen.
- Titrate basal insulin.
- Titrate prandial insulin (insulin lispro or LY900014).
- Patients will discontinue study insulins at Week 26.
- Eligible patients will have visits at approximately 3-month intervals for up to 26 weeks after Visit 801 for follow-up of insulin lispro antibody levels (see Appendix 8).

Figure ITRN.1. Illustration of study design for Clinical Protocol I8B-MC-ITRN.

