5. To compare LY900014 and insulin lispro with respect to the rate of severe hypoglycemic events	5. Rate (events/patient/100 years) of severe hypoglycemic events from baseline through Week 26
6. To compare LY900014 and insulin lispro with respect to the incidence and rate of documented symptomatic postmeal hypoglycemia	6. Rate (events/patient/year and/or events/patient/30 days) and incidence (percent of patients with at least 1 event) of documented symptomatic postmeal hypoglycemia within 1 and 2 hours after start of a meal from baseline through Week 26
7. To compare LY900014 and insulin lispro with respect to the incidence and rate of documented symptomatic hypoglycemia	7. Rate (events/patient/year and/or events/patient/30 days) and incidence (percent of patients with at least 1 event) of documented symptomatic hypoglycemic events from baseline through Week 26
8. To compare LY900014 and insulin lispro with respect to 1,5-AG	8. Change from baseline 1,5-AG values at Week 26
9. To compare LY900014 and insulin lispro with respect to 10-point SMBG profiles	9. Change from baseline 10-point SMBG values at Week 26

Objectives and Endpoints

Objectives	Endpoints
Other Secondary Objectives (Continued)	
10. To compare LY900014 and insulin lispro with respect to total, basal, and prandial insulin dose	10. Change from baseline in total, basal and prandial insulin dose and prandial/total insulin dose ratio at Week 26
11. To compare LY900014 and insulin lispro with respect to diabetes treatment satisfaction as measured by the ITSQ	11. Change from baseline ITSQ regimen inconvenience and lifestyle flexibility domain scores at Week 26
12. To compare LY900014 and insulin lispro with respect to the proportion of patients achieving HbA1c targets	12. The proportion of patients with HbA1c <7% and ≤6.5% at Week 26
Tertiary/Exploratory Objectives	
13. To compare the safety of LY900014 relative to insulin lispro	13. Adverse events, vital signs, chemistry, and hematology laboratory measures
14. To compare the incidence of treatment-emergent anti-insulin lispro antibodies for LY900014 and insulin lispro	14. Incidence of treatment-emergent positive anti-insulin lispro antibodies
15. To compare LY900014 and insulin lispro with respect to quality of life as measured by the EQ-5D-5L	15. Change from baseline in EQ-5D-5L UK-population based health state index score and EQ-VAS score at Week 26

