Study Period/Analysis	Patient Population	Baseline Observations	Post-Baseline Observations
1,5-AG	All Randomized Patients with a baseline and at least one post-baseline observation	Visit 8 prior to initiation of IP	Visits 11, 15, and 18 prior to discontinuation of IP AND Last of Visits 9-18 prior to discontinuation of IP
Health outcomes: ITSQ, EQ-5D-5L, EQ-VAS, WPAI-GH	All Randomized Patients with a baseline and a post-baseline observation	Last of Visits 1-8	Last of Visits 9-18 prior to discontinuation of IP
Safety Laboratory Tests (chemistry, hematology, lipids) – continuous analysis	All Patients in the Safety Population with a baseline and a post-baseline observation	Last of Visit 1-8	Visit 18 (planned) AND last of Visits 9-18 (planned including early discontinuation visits) regardless of IP use
Safety Laboratory Tests (chemistry, hematology, lipids) – categorical analysis	All Patients in the Safety Population with a normal baseline (with respect to the direction being analyzed) and a post-baseline observation	Visits 1-8 (including unplanned tests)	Visits 9-18 (including unplanned tests) regardless of IP use
TEAEs	All Patients in the Safety Population	Prior to first dose of randomized IP (or Visit 8 date if the dose date is missing) but after the first dose of open-label insulin lispro in the Lead-in Period	From first dose of randomized IP to last dose of randomized IP AND From first dose of randomized IP to Visit 801
Hypoglycemia events	Safety Population	All Visits 2-8	All Visits 9-18 prior to discontinuation of IP
Weight and vital signs	All Patients in the Safety Population with a baseline and a post-baseline observation	Last of Visits 2-8	Visits 9-18 prior to discontinuation of IP AND Visits 9-801 regardless of IP use
Anti-insulin lispro antibodies	Safety Population	Visit 2	Visits 3-801 regardless of IP use

Abbreviations: 1,5-AG = 1,5-Anhydroglucitol; ANCOVA = analysis of covariance; EQ-5D-5L = European Quality of Life - 5 Dimensions 5 Level; EQ-VAS = EuroQol visual analogue scale; HbA1c = hemoglobin A1c; IP = investigational product; ITSQ = Insulin Treatment Satisfaction Questionnaire; ITT = intention-to-treat; LOCF – last-observation-carried forward; MMTT = mixed meal tolerance test; MMRM = mixed-effect model repeated measures; PPG = postprandial glucose; SMBG = self-monitored blood glucose; TEAE = treatment-emergent adverse event; WPAI-GH = Work Productivity and Activity Impairment General Health.

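### The objective 14 antibody comparison counts responses that arise in the open-label lispro lead-in, before randomization, and so dilutes any difference between arms

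*SAP*

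**What the plan says.** Objective 14 (SAP Table 4.1, tertiary/exploratory) is comparative: "To compare the incidence of treatment-emergent anti-insulin lispro antibodies for LY900014 and insulin lispro". Its endpoint is "Incidence of treatment-emergent positive anti-insulin lispro antibodies".

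SAP 6.12.7 fixes the reference level: "the blood sample result at Visit 2 will be considered as the anti-insulin lispro level at baseline for this study". It chooses Visit 2 because that sample precedes the first study-provided prandial insulin. In SAP Table 6.2 the post-baseline entry for antibodies is "Visits 3-801 regardless of IP use". SAP 6.12.7.1 then states that "patients with positive TEADA response during the analysis period of Visit 2 to Visit 801 will be summarized by treatment group", with Fisher's exact test between treatment groups. The numeric criteria for a treatment-emergent response (TEADA) are redacted.

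Protocol 5.1 transfers patients on other prandial insulins to lispro at Visit 2 "so that all patients will be treated with insulin lispro throughout the lead-in period". The Schedule of Activities takes antibody samples at Visit 2, at Visit 8 and at later visits. Its randomization footnote places randomization after all Visit 8 procedures.

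SAP 6.12.7.1 uses the same window for the repeated-measures model and the maximum-value ANCOVA of percent binding. It also plans subgroup analyses of HbA1c, postprandial glucose excursions, insulin dose, hypoglycemia and selected reactions that "will be performed by the TEADA status during the analysis period of Visit 2 to Visit 801".

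**The concern.** Visit 2 is a sensible reference if the question is response since the first study-provided lispro. It is a poor place to open the event window if the question is whether LY900014 provokes more antibody than lispro. Whatever arises between Visit 2 and Visit 8 arises on the same open-label product in everyone and cannot be caused by assignment. Adding those cases to both arms moves the difference and the ratio toward none, which is the unfavourable direction in a safety comparison of a new formulation.

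The plan handles adverse events differently. In Table 6.2 the baseline for treatment-period events ends at the first randomized dose, and Table 6.5 tabulates lead-in events separately under open-label lispro. The text plans no corresponding antibody analysis restricted to responses that are new after randomization.

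**Working it through.** **Plan's own figures.** The documents give no rate, target difference or power for TEADA. The only design calculation is HbA1c noninferiority power (284 per arm, margin 0.4%, SD 1.1%). It reproduces at 99.1%, consistent with the stated 99%, but has no bearing here.

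**Step 1: does a lead-in response count?**
- The reference is Visit 2 (SAP 6.12.7).
- The Visit 8 sample is post-baseline (SAP Table 6.2) but pre-randomization (Schedule of Activities).
- A patient first meeting the criterion at Visit 8 is therefore an objective 14 event.
- If the response persists, the patient also qualifies at later visits, because the reference remains Visit 2.

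**Step 2: effect on the estimate.** Let L be the share TEADA-positive at Visit 8, equal in expectation in both arms. Let qT and qC be the shares newly positive after randomization among Visit 8 negatives. The planned incidence in each arm is

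p = L + (1-L)q,

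so the planned difference is pT - pC = (1-L)(qT - qC). This is algebra and needs no antibody data.

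**Step 3: size under assumed rates.** Inputs from the documents:
- 670 randomized 1:1, so 335 per arm, taking all as dosed and sampled;
- two-sided alpha 0.05;
- Fisher's exact test.

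Assumed inputs: qT = 25%, qC = 15%, and L as shown. Example at L=10%: pT = 0.10 + 0.90 × 0.25 = 32.5%; pC = 0.10 + 0.90 × 0.15 = 23.5%; difference 9.0 points; ratio 32.5/23.5 = 1.38. Power is exact. The last column counts only post-randomization events among Visit 8 negatives, about 335(1-L) per arm.

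| L | Planned incidence | Difference (points) | Ratio | Power as planned | Power, post-randomization events |
|---|---|---|---|---|---|
| 0% | 25.0% vs 15.0% | 10.0 | 1.67 | 0.89 | 0.89 |
| 2% | 26.5% vs 16.7% | 9.8 | 1.59 | 0.85 | 0.88 |
| 5% | 28.75% vs 19.25% | 9.5 | 1.49 | 0.80 | 0.87 |
| 10% | 32.5% vs 23.5% | 9.0 | 1.38 | 0.71 | 0.85 |
| 20% | 40.0% vs 32.0% | 8.0 | 1.25 | 0.55 | 0.80 |

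At 20% versus 12% the pattern is the same: L=10% gives 0.55 as planned against 0.74.

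**Step 4: validity under no effect.** With incidence 36% in both arms (L=20%, q=20%: 0.20 + 0.80 × 0.20), the exact size of the Fisher test is 0.041. It does not exceed 0.05.

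**Step 5: how equal are the lead-in cases?** The 95% range of the chance imbalance is ±1.96 × sqrt(2L(1-L)/335). That is ±3.3 points at L=5% and ±6.1 points at L=20%. The arms are balanced only in expectation.

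**Step 6: the related analyses.**
- The repeated-measures model can take the Visit 8 value as a response, but its visit-by-treatment terms keep that contrast apart from later visits.
- The maximum-value ANCOVA has no visit term, so a maximum reached at Visit 8 enters the treatment comparison directly.
- TEADA status through Visit 801 (Week 30) can label a patient positive for Week 26 HbA1c and glucose outcomes on the strength of a later sample.

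**The case against.** The strongest reply is that the Visit 2 baseline is deliberate and reasoned. Both arms contain insulin lispro, and cumulative response since the first study-provided lispro is a legitimate quantity. Objective 14 is exploratory, carries no multiplicity adjustment and has no power target to miss. L may be small: patients had at least 90 days of prior insulin, and lispro was an allowed prior prandial insulin, so for some of them the lead-in is not new exposure. At L=1% the loss is trivial (0.87 against 0.88). A planned listing of TEADA status by visit also lets lead-in positives be identified.

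All of that stands, and it limits the priority. It does not answer the point: the stated purpose is a between-arm comparison, the reason given for Visit 2 supports a reference level rather than an event window, and a listing is not a comparison.

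A reader might go further and infer three things that the documents do not support:
- **That identical cases are added to each arm.** They are different patients, equal in number only in expectation (Step 5).
- **That a real difference is being hidden.** Nothing in the documents shows that one exists; the plan would attenuate one if it did.
- **That the test is invalid.** Its type I error is preserved (Step 4).

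**Conclusion.** The comparison as planned counts pre-randomization responses as events and reduces the risk difference to (1-L) times its post-randomization value, with a matching loss of power. The direction and the factor follow from the design. The size does not, because L and the incidence rates are assumptions: the power loss is about 3 points at L=2%, 14 at L=10% and 25 at L=20% in the 25% versus 15% scenario. The issue concerns how informative an exploratory safety comparison is, not the validity of a test or of any primary or multiplicity-adjusted conclusion. The repeated-measures point is minor. The correction is worth making because it is cheap.

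**What to change.** - **Main comparison.** Base the objective 14 Fisher test on TEADA arising after the first dose of randomized IP, using the last pre-dose (Visit 8) sample as reference and only post-randomization samples.
- **Why the reference must move.** Dropping the Visit 8 sample from the window is not enough, because a persisting lead-in response would still qualify later against Visit 2. Excluding Visit 8 positives while keeping the Visit 2 reference would still credit sub-threshold lead-in rises to the randomized period, and would lose any boosting in patients already positive. The last power column in the table rests on Visit 8 negatives only, so it is a guide to this analysis and not its exact power.
- **Keep and add.** Retain the Visit 2 to Visit 801 table as supportive, and report lead-in TEADA (Visit 2 to Visit 8) separately by arm.
- **Percent binding.** Take only post-randomization samples as responses in the repeated-measures model and the maximum-value ANCOVA.
- **Subgroups.** For Week 26 HbA1c and postprandial glucose, define TEADA status from samples up to Visit 18. This is still a subgroup formed after randomization and should be read as descriptive.

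The cost is SAP wording, one derived flag and one more table, settled before unblinding. The drawback is that the comparison's reference level would differ from the Visit 2 baseline used for antibody follow-up, which the SAP should state.

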13. To compare the safety of LY900014 relative to insulin lispro	13. Adverse events, vital signs, chemistry, and hematology laboratory measures
14. To compare the incidence of treatment-emergent anti-insulin lispro antibodies for LY900014 and insulin lispro	14. Incidence of treatment-emergent positive anti-insulin lispro antibodies
15. To compare LY900014 and insulin lispro with respect to quality of life as measured by the EQ-5D-5L	15. Change from baseline in EQ-5D-5L UK-population based health state index score and EQ-VAS score at Week 26
16. To compare LY900014 and insulin lispro with respect to the impact that diabetes has on the ability to work and perform regular activities as measured by the WPAI-GH	16. Change from baseline in WPAI-GH item scores at Week 26
17. To compare LY900014 and insulin lispro with respect to changes in body weight	17. Change from baseline to Week 26 in weight (kg)
18. To compare LY900014 and insulin lispro with respect to the proportion of patients achieving improvement from baseline HbA1c targets	18. The proportion of patients with shifts in HbA1c to <8% and ≤9%, and >9% from baseline to Week 26
19. To compare LY900014 and insulin lispro with respect to glycemic variability	19. Within-day and between-day glycemic variability measured by the standard deviation and the coefficient of variation of 10-point SMBG profiles

Abbreviations: 1,5-AG = 1,5-Anhydroglucitol; EQ-5D-5L = European Quality of Life – 5 Dimensions 5 Level; EQ-VAS = EuroQol visual analog scale; HbA1c = hemoglobin A1c; ITSQ = Insulin Treatment Satisfaction Questionnaire; MMTT = mixed-meal tolerance test; NIM = noninferiority margin; PPG = postprandial glucose; SMBG = self-monitored blood glucose; T2D = type 2 diabetes; WPAI-GH = Work Productivity and Activity Impairment Questionnaire General Health.

5. Study Design

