6.1. General Considerations

Statistical analysis of this study will be the responsibility of Eli Lilly and Company (hereafter Lilly). Any change to the data analysis methods described in the protocol will require an amendment ONLY if it changes a principal feature of the protocol. Any other change to the data analysis methods described in the protocol, and the justification for making the change, will be described in this SAP and/or in the clinical study report (CSR). Additional exploratory analyses will be conducted, as deemed appropriate.

Statistical analyses for Japan are described in [Appendix 2](#). Statistical Analyses for the Maximum Extended Enrollment (MEE) Addendum are described in [Appendix 3](#).

For purposes of analysis, the following populations are defined in [Table 6.1](#):

Table 6.1. Patient Populations

Population	Description
Entered	All patients who give informed consent.
Enrolled	All patients who receive at least 1 dose of open-label insulin lispro in the 8-week lead-in period.
Randomized	All patients who are randomly assigned to study treatment at Visit 8. Treatment group will be defined on the basis of the treatment the patients are assigned.
Safety	All randomized patients who receive at least 1 dose of the randomly assigned investigational product (IP). Treatment group will be defined on the basis of the treatment the patients are assigned.
Completer	Patients included in the randomized population who have completed Week 26 of study treatment without permanent discontinuation of IP. Treatment group will be defined on the basis of the treatment the patients are assigned.
Per Protocol	Patients included in the randomized population who have completed Week 26 of study treatment without permanent discontinuation of IP and without significant protocol deviations through Week 26 that would significantly impact the primary objective. Treatment group will be defined on the basis of the treatment the patients actually receive.

Unless otherwise stated, the efficacy analyses will be conducted on the Randomized Population, and the safety analyses will be conducted on the Safety Population.

The primary analysis is for the treatment period through Week 26.

Unless otherwise noted, all tests of treatment effects will be conducted at a 2-sided alpha level of 0.05, and CIs will be calculated at 95%, 2-sided. All tests of interactions between treatment groups and other factors will be conducted at a 2-sided alpha level of 0.10.

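### The between-arm test of TEADA incidence (objective 14) does not use Visit 2 antibody status; it is valid, but a test stratified on that status would be somewhat more precise (minor, optional)

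*SAP*

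**What the plan says.** Objective 14 (Protocol section 4, Table ITRN.1; SAP Table 4.1) is tertiary/exploratory. Its endpoint is "Incidence of treatment-emergent positive anti-insulin lispro antibodies".

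SAP 6.12.7 plans the baseline sample for everyone: "Blood samples for immunogenicity testing will be collected to determine antibody production against insulin lispro for all enrolled patients since Visit 2". It also fixes the reference point: "the blood sample result at Visit 2 will be considered as the anti-insulin lispro level at baseline for this study".

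SAP 6.12.7.1 defines TEADA as a change in percent binding from Visit 2. TEADA can be sub-classified as treatment-induced (antibody not detected at Visit 2) or treatment-boosted (antibody detected at Visit 2). The numerical cut-offs are redacted.

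The summary is of "The number and percentage of patients with positive TEADA response during the analysis period of Visit 2 to Visit 801" by treatment group, and the stated comparison is "Treatment groups will be compared by Fisher's exact test". No stratum or covariate is named for it. SAP 6.1 sets the level: "Unless otherwise noted, all tests of treatment effects will be conducted at a 2-sided alpha level of 0.05". SAP 6.5 makes no multiplicity adjustment for this objective.

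**The concern.** A patient becomes TEADA-positive by one of two routes, and Visit 2 status decides which route applies. It is reasonable to expect the chance of a positive result to differ between patients with and without detected antibody at Visit 2. Randomization is not stratified on antibody status (SAP 5.3), so any chance imbalance between the arms stays in the crude comparison.

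Elsewhere the SAP does adjust for baseline in similar situations. Hypoglycemia incidence uses logistic regression with the baseline event rate (SAP Table 6.6). The MMRM and ANCOVA of antibody percent binding include the baseline value, but they sit in a paragraph about TEADA-positive patients. The Fisher comparison is therefore the one that answers objective 14 in the full Safety population.

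Fisher's exact test also runs below its nominal level at this sample size. In a safety comparison a missed real increase is the costlier error, so precision that comes free is worth having. SAP 6.1 lists only counts and percentages for categorical measures, and 6.12.7.1 adds no interval for the difference in TEADA incidence.

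**Working it through.** **The plan's own power figure.** The documents state no power for TEADA. The only stated power is for the primary endpoint: margin 0.4, SD 1.1, 284 per arm (Protocol 10.1, SAP 5.2). It reproduces: z = 0.4 / (1.1 × √(2/284)) = 4.33, and Φ(4.33 − 1.96) = 0.991, against more than 99% stated.

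**Inputs from the documents.** 670 randomized 1:1, so 335 per arm; two-sided 0.05; Fisher's exact test.

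**Assumed inputs, not in the documents.** Share detected at Visit 2 of 20%, 40% or 60%; control TEADA rates by Visit 2 status; a common odds ratio (OR) of 1.6.

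**Method.** Each setting was simulated 20,000 times. Three tests were compared: Fisher's exact, Pearson chi-square without correction, and CMH stratified by Visit 2 status. Pearson minus Fisher isolates Fisher's conservatism. CMH minus Pearson isolates the value of stratifying.

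**Power with 40% detected at Visit 2** (rates are control TEADA, not detected / detected; differences in points, taken before rounding):

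| Rates | Fisher | Pearson | CMH | CMH − Fisher | Pearson − Fisher | CMH − Pearson |
|---|---|---|---|---|---|---|
| 25% / 25% | 76.4% | 79.1% | 78.9% | 2.4 | 2.6 | −0.2 |
| 20% / 30% | 74.2% | 76.8% | 77.2% | 3.0 | 2.6 | 0.4 |
| 15% / 35% | 68.8% | 71.9% | 74.3% | 5.6 | 3.1 | 2.5 |
| 10% / 40% | 59.1% | 62.6% | 69.3% | 10.3 | 3.5 | 6.8 |
| 35% / 10% | 68.1% | 70.9% | 75.0% | 6.9 | 2.8 | 4.1 |
| 5% / 50% | 41.9% | 45.5% | 59.2% | 17.3 | 3.5 | 13.8 |

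**Type I error.** With OR 1, Fisher rejected in 3.8% to 4.4% of trials and CMH in 4.8% to 5.4%.

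**Hand check of the 10% / 40% row.**

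1. Treated rates from OR 1.6: odds 0.1111 × 1.6 = 0.1778, rate 0.1509; odds 0.6667 × 1.6 = 1.0667, rate 0.5161.
2. Overall rates: control 0.4 × 0.40 + 0.6 × 0.10 = 0.220; treated 0.4 × 0.5161 + 0.6 × 0.1509 = 0.297.
3. Pearson: mean rate 0.2585, z = 0.0770 / √(2 × 0.2585 × 0.7415 / 335) = 2.28, power Φ(2.28 − 1.96) ≈ 0.62.
4. CMH strata hold 134 detected and 201 not detected per arm. Numerator: 67 × 0.1161 + 100.5 × 0.0509 = 12.90.
5. CMH variance, with the N/(N − 1) factor: 16.69 + 11.06 = 27.75. So z = 12.90 / √27.75 = 2.45, power Φ(2.45 − 1.96) ≈ 0.69.

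These agree with the simulated 62.6% and 69.3%.

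**Range across 20%, 40% and 60% detected.** Leaving out the extreme 5% / 50% setting, the total gain over Fisher is 2.1 to 10.3 points. Of that, 2.2 to 3.9 come from Fisher's conservatism and about 0 to 6.8 from stratification. At 5% / 50% the total is 15.0 to 17.3. With lower TEADA rates and OR 2.2 it is 4.8 to 18.6. CMH never had less power than Fisher in these settings.

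**The case against.** The strongest reply is that nothing here is wrong. The test controls type I error. With 1:1 randomization, leaving out a baseline covariate costs precision and does not bias the comparison. Objective 14 is exploratory, carries no power claim, and is reported with numbers and percentages by arm and a full antibody listing. Fisher's or Pearson's test is the SAP's general method for categorical measures (SAP 6.1), so its use here is consistent. All of that stands, and it is why the point is minor.

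Three stronger readings are tempting, and the documents do not support them.

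- A reader might infer that the whole loss comes from leaving out Visit 2 status. It does not: in the 25% / 25% row status is not prognostic, stratifying adds nothing, and the gain is all Fisher's conservatism. An unadjusted Pearson test would recover that part.
- A reader might take 2 to 10 points as a property of this trial. The documents give neither TEADA rates nor the detected share, the cut-offs that would shape any association are redacted, and the odds ratio is assumed.
- A reader might infer that Visit 2 data are ignored altogether. They are built into the TEADA definition; only the test leaves them out.

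Two more limits stand. The analysis window starts at Visit 2 and so includes the 8-week open-label lispro lead-in, which the simulation does not model separately. The gain also relies on a common odds ratio: at 10% / 40%, with an odds ratio of 2.2 in the not-detected stratum and 1.0 in the other, CMH gained only about 1.6 points over Pearson.

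**Conclusion.** The point holds as a minor, optional improvement in precision. The planned test is valid and unbiased; it just does not use a baseline variable that is planned for all enrolled patients and already divides the endpoint into its two subtypes.

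For control rates that differ by up to 30 points between Visit 2 strata, at 335 per arm and an odds ratio of 1.6, the stratified test gains about 2 to 10 points of power. Roughly 3 of these come from moving off a test whose actual size is about 4%, and 0 to 7 from stratification. A gain well above 10 points needs a very strong association or low rates with a larger effect. The direction does not depend on the particular rates tried; the size does.

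**What to change.** In SAP 6.12.7.1, make the between-arm comparison of TEADA incidence a Cochran-Mantel-Haenszel test stratified by Visit 2 antibody status (detected / not detected). Report the Mantel-Haenszel risk difference with its 95% CI, which is useful for a safety question whatever the p-value. Keep Fisher's exact test as a supportive check.

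Do not leave an open-ended option to switch to an exact stratified test when events are few. Either omit it or fix its trigger in advance. An exact version brings conservatism back: with a continuity-corrected CMH as a rough stand-in, at 40% detected, the gain over Fisher was −0.1, 0.3, 2.6 and 6.7 points in the first four rows of the table.

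The cost is a sentence or two in the SAP before unblinding, with no new data. Detected / not-detected status is already in the planned antibody listing. Patients without a Visit 2 result cannot be stratified, but they cannot be classified for TEADA either. Protocol 10.3.4 leaves immunogenicity methods to the SAP.
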